### 7.2.1.3 Adverse Event and Serious Adverse Event Reporting

All AEs, serious and non-serious, occurring during the course of the clinical trial (i.e., from signing the informed consent through the follow-up period) will be collected, documented, and reported to the sponsor by the investigator on the appropriate eCRF and SAE reporting forms.

For each AE, the investigator will provide the onset date, end date, seriousness, grade, relatedness, treatment required, outcome, and action taken with the study agent. The investigator will determine the grade as defined in [Section 7.2.1.2.3](#) and the causal relationship to the study agent (relatedness) as defined in [Section 7.2.1.2.4](#).

The investigator must report the following events immediately (within 24 hours or the next business day whichever is shorter) to the sponsor or designee (refer to the Lab Manual/ISF for specific instructions): SAEs and non-serious AEs relevant to the reported SAE and protocol-specified AESI.

The investigator does not need to actively monitor subjects for adverse events once the clinical trial has ended. However, if the investigator becomes aware of an SAE(s) that occurred after the subject has completed the clinical trial, it should be reported by the investigator to the sponsor if considered relevant by the investigator.

Any AE occurring during the study must be documented in the subject's medical records and as an AE in the eCRF. Any SAE occurring during the study must be documented in the subject's medical records and as an SAE in the eCRF.

A separate SAE report should be used for each SAE. However, if at the time of initial reporting, multiple SAEs are present that are temporally and/or clinically related, they may be reported on the same SAE report.

The investigator should attempt to establish a diagnosis of the event (that meets the definition of an AE or SAE) based on signs, symptoms, and/or other clinical information. In such cases, the diagnosis should be

documented as the AE and/or SAE and not the individual signs or symptoms. The diagnosis will become the basis for the verbatim term as reported by the investigator. If no diagnosis is known and clinical signs and symptoms are not present, the abnormal finding should be recorded.

The investigator will take all appropriate and necessary therapeutic measures required for resolution of the AE. Any medication necessary for the treatment of an AE must be recorded on the concomitant medication case report form.

The SAE report(s) should be completed as thoroughly as possible and signed by the investigator or his/her designee before transmittal to the sponsor or designee (e.g., study CRO). It is very important that the investigator provide his/her assessment of relatedness to the study agent as well as an applicable diagnosis at the time of the initial SAE report.

---

**7.2.2 SAFETY LABORATORY EVALUATIONS**

Blood samples and urine must be collected at every visit. Safety laboratory examinations will include hematology, biochemistry, coagulation and qualitative urine analysis.

- Hematology: hemoglobin, red blood cell count (RBC), white blood cell count (WBC) with differential, platelets
- Biochemistry: glucose, sodium, potassium, calcium, inorganic phosphate, creatinine, aspartate aminotransferase (AST), alanine aminotransferase (ALT), alkaline phosphatase (AP), lactate dehydrogenase (LDH), total bilirubin (if elevated provide direct bilirubin), urea, total protein, albumin, uric acid
- Coagulation: activated partial thromboplastin time (aPTT), prothrombin time (PT)/international normalized ratio (INR)
- Urine: potential of hydrogen (pH), glucose, erythrocytes, leukocytes, protein, nitrite

Glomerular filtration rate (GFR) will be estimated by the Cockcroft Gault Formula utilizing serum creatinine (see [Section 17.5](#)). All safety laboratory measurements will be performed by a central laboratory. Investigators will get guidance and instructions on laboratory sampling and processing through a separate Lab Manual provided by the central laboratory.

The investigator is responsible for determining and documenting if out of range laboratory values are clinically significant or not. All clinically significant values will be recorded as AEs in the eCRF and followed until resolution. Once resolved, the appropriate eCRF page(s) will be updated.

---

**7.2.3 ELECTROCARDIOGRAM**

Twelve-lead ECGs (I, II, III, aVR, aVL, aVF, V1 - V6) will be recorded using a computerized electrocardiograph. The ECGs will be recorded for a 10-second duration after the subjects have rested for at least 5 minutes in a supine position (see [Section 15.1, Schedule of Events Table](#), for time points). ECGs will be stored in the subject's medical records. ECGs may be repeated for quality reasons and the repeat ECG will be used for analysis. Additional ECGs may be collected by the investigator for safety reasons. Abnormal findings will be reported as AEs (during the trial) or baseline conditions (at screening) in the eCRF.

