9.3 Visit Windows and Visit Mapping

The following table lists the scheduled visits and planned study day along with the corresponding visit window that will be used to map visits occurring outside of the scheduled times.

Scheduled Visit	Planned Study Day	Visit Window
Visit 1 / Screening	Day -7*	<= Day -1
Visit 2	Day 1	Day 1
Visit 3	Day 8	Day 2 to Day 11
Visit 4	Day 15	Day 12 to Day 18
Visit 5	Day 22	Day 19 to Day 25
Visit 6	Day 29	Day 26 to Day 32
Visit 7	Day 36	Day 33 to Day 39
Visit 8 / End of Treatment (EOT)	Day 43	Day 40 to Day 46
Visit 9 / Follow-Up (FU)	Day 50	Day 47 to Day 53
Visit 10 / FU	Day 57	Day 54 to Day 60
Phone / FU	Day 71	>=Day 61

* Visit 1/Screening of Fundus Photography/FA can be performed up to Day -14, per the protocol.

Summary tables will be presented by scheduled visit using the following algorithm. If there are multiple non-missing assessments within a visit window, then the visit closest to the scheduled visit will be used. If multiple visits are equidistant from the scheduled visit, then the scheduled visit and unscheduled visit

will be selected in that order. If multiple visits of the same type are equidistant from the scheduled window, then the earliest visit of that type will be selected.

Subject listings will include all visits.

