16.5 Electrocardiogram (ECG)

ECGs will be measured at screening Visit 1, Visit 3, Visit 6, and Visit 8/EOT, and graded as normal or abnormal. Abnormal findings or changes from baseline will be further classified as not clinically significant (NCS) or clinically significant (CS). In the event abnormal ECG results requires additional follow up, ECGs may be performed at unscheduled visits or at a study visit that an ECG is not required per protocol. ECG data performed outside of the protocol specified time points will be captured in the EDC on an "Unscheduled Visit" eCRF and mapped to the nearest scheduled visit as defined in [Section 9.3](#). ECG grades and shift from baseline will be summarized with counts and percentages for each visit for the Safety set. All clinically significant findings will be recorded as AEs in the eCRF and followed until resolution. Once resolved, the AE eCRF page(s) will be updated. A subject listing of the ECG results will also be produced.

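### Protocol 7.2.3 has the quality-repeat ECG analysed, but SAP 9.3 makes no such exception and can select the first tracing; unselected unscheduled ECG and laboratory values also have no place in the safety tables

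*Protocol*

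**What the plan says.** Protocol 7.2.3 deals with two kinds of extra ECG. For technical repeats: "ECGs may be repeated for quality reasons and the repeat ECG will be used for analysis". For clinical ones: "Additional ECGs may be collected by the investigator for safety reasons".

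SAP 9.3 sets one selection rule for all by-visit summaries, in three steps:

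1. "If there are multiple non-missing assessments within a visit window, then the visit closest to the scheduled visit will be used".
2. "If multiple visits are equidistant from the scheduled visit, then the scheduled visit and unscheduled visit" are taken in that order.
3. "If multiple visits of the same type are equidistant from the scheduled window, then the earliest visit of that type will be selected".

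SAP 16.5 says that ECGs done outside the protocol time points are captured on an unscheduled-visit form and "mapped to the nearest scheduled visit as defined in" SAP 9.3. On output it says: "ECG grades and shift from baseline will be summarized with counts and percentages for each visit for the Safety set". The planned ECG tables are 14.3.12.1 (overall results) and 14.3.12.2 (shift). The laboratory tables in the 14.3.10 series are likewise summaries and shifts.

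Four other provisions matter:

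- SAP section 1 gives the SAP's analysis methods precedence over the protocol's.
- SAP section 21, on changes from protocol-stated analyses, reads as not applicable.
- SAP 9.2 takes the last measure before treatment as baseline.
- SAP 9.3 puts all visits in the listings.

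**The concern.** The protocol decides which tracing counts when one is repeated because it was technically poor. The SAP has a general rule that never mentions this case and whose tie-breaks point the other way: scheduled before unscheduled, and earlier before later. A programmer working from the SAP, which takes precedence, would have no instruction to prefer the repeat. The protocol rule would then be reversed without anyone having chosen to reverse it, and the change would not be declared.

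A second, separate gap comes from the same rule. It keeps one record per window. Unscheduled ECGs and laboratory tests tend to be taken because something looked wrong: Protocol 7.2.3 allows safety ECGs, and Protocol 17.1.2.6 asks for at least weekly repeat liver tests after a hepatic signal. When such a value shares a window with a closer scheduled value, it is not tabulated at that visit, and no planned ECG or laboratory table shows the worst post-baseline value.

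At stake is whether the ECG and laboratory tables use the intended record and show the most abnormal results. Efficacy conclusions are not affected.

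**Working it through.** The plan gives no figure on this point to reproduce. The check applies the SAP 9.3 rule to a first tracing and a later repeat.

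**Inputs.** ECGs after baseline are planned at Visits 3, 6 and 8 (Days 8, 29 and 43), each ±1 day (SAP 4.2). The SAP 9.3 mapping windows are Days 2 to 11, 26 to 32 and 40 to 46. The first tracing is a scheduled record at −1, 0 or +1 day from plan. The repeat comes 0 to 3 days later and is entered as either scheduled or unscheduled. Both are taken as graded, non-missing records.

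**Rule.** Choose the smallest |record day − planned day|, then scheduled before unscheduled, then the earlier record.

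**Record selected** (the same at all three visits and for both ways of entering the repeat):

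| Repeat taken | First tracing at −1 day | First tracing on planned day | First tracing at +1 day |
|---|---|---|---|
| Same day | first | first | first |
| 1 day later | repeat (0 v 1 day) | first | first |
| 2 days later | first (tie at 1 day) | first | first |
| 3 days later | first | first | first; the repeat falls in the next visit's window |

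For a same-day repeat, the first tracing is selected in 3 of 3 positions. If the repeat is entered as unscheduled, step 2 decides. If both tracings are entered under the scheduled visit, step 3 decides, and earliest must then be read as clock time because the dates are equal.

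**Cases with no error.** If the rejected tracing is not entered, or has no normal/abnormal grade, it is missing for step 1 and the repeat is selected. At baseline, SAP 9.2 takes the last pre-treatment record, which is the repeat, as the protocol intends.

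**Size.** Planned post-baseline ECGs: 30 subjects × 3 visits = 90. The documents give no repeat rate. Assuming 0% to 5%:

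- 0% × 90 = 0 records
- 2% × 90 = 1.8 records
- 5% × 90 = 4.5 records, about 5

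The upper end also assumes that every rejected tracing is entered with a grade and is then selected. Any one subject misclassified in a 30-subject table moves a percentage by 1/30 = 3.3 points.

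**Unscheduled values.** An unscheduled ECG on Day 15, where none is planned, is the only record in the Visit 4 window and is tabulated at Visit 4. By contrast, a laboratory retest on Day 17 is 2 days from plan. It loses to a scheduled Day 15 sample at 0 days and is not shown in the Visit 4 summary or shift.

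**The case against.** The strongest reply is that SAP 9.3 speaks of visits, not of tracings within a visit. On that reading a same-visit repeat is not a second visit, Protocol 7.2.3 settles which tracing is the visit's ECG, and SAP 9.3 runs afterwards. The entry in SAP section 21 fits, since no change was intended. SAP 16.5 can also be read as covering follow-up of abnormal ECGs rather than technical repeats at a planned visit. This reading is reasonable, but the SAP does not state it. SAP 9.3 opens with assessments, not visits, and a repeat entered on the unscheduled form would be treated as a separate record. The ambiguity stands.

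Several stronger conclusions might be inferred, and the documents do not support them:

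- *Rejected tracings will be analysed.* Only if they are entered as graded records, which the documents do not say.
- *The SAP simply picks the earliest record.* That is the last tie-break, after closeness and visit type.
- *Unscheduled values are left out of by-visit tables.* SAP 16.5 maps unscheduled ECGs in. A value is lost from a table only when another record in its window is selected.
- *Abnormal values are lost.* They remain in the listings. SAP 16.5 records clinically significant ECG findings as AEs, and SAP 16.4 does the same for laboratory values. QTc prolongation and hepatic injury are AESIs with numeric thresholds (SAP 16.1), so they do not rest on an investigator's judgement alone.
- *IOP shifts are affected.* No IOP shift table is planned. SAP 16.3 counts subjects at or above 20 and 30 mmHg but does not say which records feed the counts.

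It is also fair to say that no document promises a worst post-baseline summary, and that safety analysis here is descriptive in about 30 subjects. Its absence is not an error, and adding it is an improvement.

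**Conclusion.** The point holds in a limited form and is minor. Read literally, SAP 9.3 selects the first of two graded same-day ECGs, where Protocol 7.2.3 calls for the repeat, and SAP section 21 does not declare the difference. The effect is 0 to about 5 of 90 planned post-baseline ECGs. This rests on an assumed repeat rate of 0% to 5% and, at the upper end, on sites entering rejected tracings with a grade. Baseline is unaffected.

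Separately, unscheduled ECG and laboratory values can drop out of the by-visit and shift tables. An abnormal value that is not selected and is judged not clinically significant, and that is not an AESI, would then appear only in a listing. How often this would happen cannot be worked out from the documents.

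**What to change.** Add one sentence to SAP 9.3 or 16.5, for example: *Where an ECG is repeated for quality reasons, the repeat replaces the rejected tracing before the visit-window rule is applied (Protocol 7.2.3).*

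Add a worst post-baseline row to the ECG shift table (14.3.12.2) and the laboratory shift tables (14.3.10.1.2, 14.3.10.2.2 and 14.3.10.3.2), using all scheduled and unscheduled records once quality repeats have been substituted. State in SAP 16.3 that the two IOP threshold counts use any post-baseline record, scheduled or unscheduled.

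No new data are needed. The cost is a little extra programming and a safety summary that looks slightly less favourable, because it shows each subject's most abnormal value.

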**7.2.4 VITAL SIGNS AND PHYSICAL EXAMINATION**

**7.2.4.1 Vital Signs**

Vital signs (blood pressure, pulse rate and respirations) and temperature will be recorded according to [Section 15.1, Schedule of Events Table](#).

**7.2.4.2 Physical Examination**

A general physical examination including height (measured only at screening) and weight will be performed according to the time points in [Section 15.1, Schedule of Events Table](#). Whenever possible, the same health care practitioner should perform this examination.

**7.2.5 OTHER OPHTHALMIC EXPLORATORY ENDPOINTS AND EVALUATIONS**

The ophthalmic endpoints described below as being evaluated over time will be measured in an exploratory manner to investigate the extent, onset, and duration of action without specific inferential testing at any time point. The same is valid for endpoints described as change from baseline.

- CST as measured by SD-OCT, absolute and as change from baseline
- Presence and height of IRF by SD-OCT over time, absolute and as change from baseline
- Presence and height of SRF by SD-OCT over time, absolute and as change from baseline
- Presence and height of PED by SD-OCT over time, absolute and as change from baseline
- Neovascular leakage as demonstrated by fundus photography/FA, absolute and as change from baseline
- Vascular area measured by SD-OCT and fundus photography/FA, absolute and as change from baseline

**7.2.5.1 Optical Coherence Tomography**

The retinal layers and thickness can be visualized and measured by OCT. The study eye will be investigated by a trained person using only specified OCT equipment. A detailed manual for OCT image acquisition and data transmission will be provided in the ISF. The reported CST will be exclusive of the sub-RPE layer fluid.

**7.2.5.2 Fundus Photography/Fluorescein Angiography**

The retinal vasculature of the study eye will be evaluated and imaged by fundus photography/FA. A detailed manual for fundus photography/FA will be provided in the ISF.

**7.2.5.3 Slit Lamp and Intraocular Pressure Measurement**

The slit lamp examination is to be performed in both eyes. The anterior and posterior segment of the eye should be assessed. The results will be entered in the eCRF. IOP will be measured using applanation Goldmann tonometry in both eyes during each visit. The results will also be entered in the eCRF.

**7.2.6 STUDY AGENT CONCENTRATION AND PHARMACOKINETICS**

Plasma concentration measurements of ALK4290 will be collected to assess systemic exposure to the study agent. For sampling time points and further details, please refer to [Section 17.3](#).

**7.2.6.1 Pharmacokinetic Endpoints**

As far as feasible, the following pharmacokinetic parameters will be derived by noncompartmental methods:

- $C_{max}$  Maximum concentration of ALK4290 in plasma after single dose
- $t_{max}$  Time of  $C_{max}$  relative to last dosing
- $t_{max,ss}$  Time of  $C_{max,ss}$  relative to last dosing
- $C_{pre,ss,N}$  Pre-dose concentration of ALK4290 in plasma immediately before administration of the Nth dose

In addition, the average pre-dose concentration in plasma at steady state will be calculated as the geometric mean of  $C_{pre,ss,N}$  values.

**7.2.6.2 Methods of Sample Collections**

For quantification of ALK4290 plasma concentrations and for biomarker investigations (see [Section 7.2.8](#)), one blood sample of approximately 6 mL per sampling time point (see [Section 17.2.1, Table of Pharmacokinetic, Biomarker, and Pharmacogenomic Sampling](#)) will be taken from an antecubital or forearm vein into a potassium ethylenediaminetetraacetic acid (EDTA)-anticoagulant blood drawing tube.

The EDTA-anticoagulated blood samples will be centrifuged to collect plasma. For pharmacokinetic samples only, the obtained plasma will be split into 2 aliquots and stored in polypropylene tubes. At the selected time points with additional biomarker determinations, 5 instead of 2 aliquots of at least 0.5 mL plasma each will be prepared from the blood sample. The time from blood collection until the transfer of plasma aliquots into the freezer should not exceed 60 minutes, with interim sample storage on wet ice whenever possible. Samples will be positioned upright and will be frozen at approximately -20°C or below until shipment. These aliquots will be processed by the central laboratory. Details of plasma collection, sample handling, and shipment instructions will be provided in the Lab Manual/ISF.

**7.2.6.3 Analytical Determinations**

Concentrations of ALK4290 and metabolites (if feasible) in plasma samples will be determined by a validated high performance liquid chromatography, tandem mass spectrometry (HPLC-MS/MS) assay. Leftover samples will be used for exploratory biomarker assessment (see [Section 7.2.8](#)).

**7.2.7 PHARMACOGENOMIC EVALUATIONS**

Pharmacogenetic analysis of prespecified genes is mandatory and a prerequisite for participation in this study.

- [REDACTED]

Prespecified analyses will be performed at the end of the trial and the data will be part of the report. All remaining samples will be destroyed after the end of the trial.

- [REDACTED]

**7.2.7.1 Methods and Timing of Sample Collection**

One blood sample of 3 mL blood for prespecified pharmacogenomic testing will be obtained at Visit 2 in a potassium EDTA-anticoagulant blood drawing tube. [REDACTED] For additional information, see [Section 17.2.1, Table of Pharmacokinetic, Biomarker, and Pharmacogenomic Sampling](#) and in the Lab Manual/ISF.

The PAXgene Blood DNA tubes and EDTA containing blood sampling tubes can be stored and shipped at room temperature within 14 days. If a longer storage and shipment period for PAXgene Blood DNA tubes is necessary, these blood samples should be stored at a temperature of -20°C or below. Once frozen, thawing of the samples should be avoided.

**7.2.7.2 Analytical Determinations**

DNA will be extracted from blood samples according to standard molecular genetics methods and analyzed by standard genotyping and gene expression technologies.

Detailed instructions for pharmacogenomic sampling, handling and shipment of samples are provided in the Lab Manual/ISF.

---

**7.2.8 BIOMARKERS**

Measurement of biomarkers is exploratory. [REDACTED]

[REDACTED]

After completion of the study, leftover samples may be used for further methodological and/or other, non-genetic biomarker investigations either by the sponsor, or designee. The study samples will be discarded after completion of the additional investigations, but not later than 3 years after the final study report has been archived.

**7.2.8.1 Method of Sample Collection**

For quantification of ALK4290 plasma concentrations (see [Section 7.2.6](#)) and for biomarker investigations, one blood sample of approximately 6 mL per sampling time point (see [Section 17.2.1, Table of Pharmacokinetic, Biomarker, and Pharmacogenomic Sampling](#) and [Section 15.1 Schedule of Events Table](#)) will be taken from an antecubital or forearm vein into a potassium EDTA-anticoagulant blood drawing tube.

The EDTA-anticoagulated blood samples will be centrifuged to collect plasma. For pharmacokinetic studies only, the obtained plasma will be split into 2 aliquots and stored in polypropylene tubes. At the selected time points with additional biomarker determinations, 5 instead of 2 aliquots of at least 0.5 mL plasma each will be prepared from the blood sample. The time from blood collection until the transfer of plasma aliquots into the freezer should not exceed 60 minutes, with interim sample storage on wet ice whenever possible. Samples will be positioned upright and will be frozen at approximately -20°C or below until shipment. These aliquots will be collected by the central laboratory. Details of plasma collection, sample handling, and shipment instructions will be given in the Lab Manual in the ISF.

**7.2.8.1 Analytical Determinations**

The exploratory biomarker measurements will be conducted either at the sponsor’s labs or at external CROs using appropriate methodology (e.g., immunoassays, multiplex technology). A Lab Manual/ISF will describe the handling of the samples.

